2 STUDY OBJECTIVES AND OUTCOMES

2.1 Study Objectives

2.1.1 **Primary Objective(s)**

The primary objective of the P-RAPP trial is to demonstrate the feasibility to efficiently and effectively enroll low-risk children with Community Acquired Pneumonia (CAP) and

Procalcitonin (PCT) levels < 0.25 into a multicenter randomized controlled trial evaluating antibiotics vs placebo, while refining study procedures for the subsequent large clinical trial.

2.2 Study Outcomes

2.2.1 Primary Outcome(s)

The primary outcome in this pilot study is the enrollment rate per site per month.

Eligibility for Primary Analysis The enrollment rate will be derived for those subjects who are randomized into the second stage of the trial.

2.2.2 Secondary Outcome(s)

Secondary outcomes of this pilot study include:

- 1. Consent and drop-out rates between the two stages of consent
- 2. Parental attitudes and beliefs about trial procedures
- 3. Feasibility and usability of video chat follow-up
- 4. Lost to follow-up rates

Eligibility for Secondary Analysis Secondary outcome 1 will include all patients who have a PCT < 0.25 from Stage I of the trial. Secondary outcome 2 will be analyzed through interview data which are collected separate from the clinical trial. Secondary outcomes 3 and 4 will be analyzed among those subjects who are randomized into Stage II of the trial.

| October 5, 2021 | SAP Version 1.00 | CONFIDENTIAL |
|-----------------|------------------|--------------|

2.2.4 Safety Outcome(s)

There are no pre-specified safety outcomes. Several exploratory outcomes capture safety events.

3 STUDY DESIGN AND METHODS

3.1 Overall Study Design

This pilot clinical trial is a 3-site, randomized, placebo-controlled, double-blinded trial. There are two stages of enrollment in this study. The first stage (Stage I) will collect data on any eligible and consented subject. Blood will be collected on these subjects in Stage I and the subjects PCT will be evaluated. If the PCT is less than 0.25 ng/mL, then the subject will be approached for consent to participate in the RCT (Stage II). If the subject is consented for Stage II, randomization is performed and the subject is enrolled into the clinical trial. Randomized subjects will be followed daily for 7 days. At 7 and 21 days after the ED visit, a follow-up phone/video call will be made to assess further outcomes for randomized subjects. After 21 days, a medical chart review will be performed to assess additional outcomes on all subjects in both Stage I and Stage II.

3.2 Method of Treatment Assignment and Randomization

After enrollment and confirmation of a PCT <0.25 ng/mL, subjects will be randomized to a 7-day course of either amoxicillin or placebo. Randomization will be stratified at a 1:1 ratio stratified by site with block sizes of 2 and 4.

3.2.1 Delivery of Randomization and Emergency Backup

Randomization will occur within the database. There are no emergency backup envelopes for this study. The randomization process will produce a randomization ID which the site coordinator will then provide to the site pharmacist (who will have a mechanism to identify arm and produce study drug).

3.3 Treatment Masking (Blinding)

The P-RAPP trial will be performed in a double-blind fashion. All study personnel, including investigators and research coordinators, shall be blinded to assigned treatment arm for each enrolled subject. Of necessity, biostatisticians involved in presenting interim analyses to the DSMB will be aware which subjects have received which arm due to the derivation of some outcomes.

Unblinded personnel in this study will include: the site research pharmacist and, possibly, a pharmacy monitor contracted by the DCC expressly for the purpose of ensuring assigned treatments have been correctly prepared and delivered in this study. The DSMB may request to be unblinded to treatment assignment at any time. If this occurs, the DCC biostatisticians will also be unblinded.

4 STUDY SUBJECTS AND ANALYSIS POPULATIONS

4.1 Eligibility

Study eligibility details can be found in the protocol.

4.2 **Populations for Analyses**

There are several populations considered for analyses. These are described in detail below.

4.2.1 Screening Population

The screening population (SCREEN) includes all subjects who are screened for eligibility into the trial, regardless of whether or not they are approached for consent for Stage I. This population represents all patients who meet inclusion criteria outlined in the study protocol. This population will be used for reporting of study flow per Consolidated Standards of Reporting Trials (CONSORT) guidelines.

4.2.2 Study Eligible Population

The study eligible population (ELIGIBLE) includes all SCREEN subjects who meet study inclusion/exclusion criteria (regardless of whether they consent in Stage I).

4.2.3 Stage I Approached Population

The Stage I approached population (STAGE I APPROACHED) includes all ELIGIBLE subjects who were approached by a study team member to participate in the study.

4.2.4 Stage I Consented Population

The Stage I consented population (STAGE I CONSENTED) includes all STAGE I AP-PROACHED subjects who have consented to get their blood draw.

4.2.5 Blood Draw Population

The blood draw population (BLOOD DRAW) includes all STAGE I CONSENTED who have a blood draw obtained to evaluate PCT.

4.2.6 **RCT Eligible Population**

The RCT eligible population (RCT ELIGIBLE) includes all BLOOD DRAW subjects whose PCT value is <0.25 ng/mL.

4.2.7 Stage II Approached Population

The Stage II approached population (STAGE II APPROACHED) includes all RCT ELIGI-BLE subjects who were approached by a study team member to participate in the RCT.

4.2.8 Stage II Consented Population

The Stage II consented population (STAGE II CONSENTED) includes all STAGE II AP-PROACHED subjects who have consented to participate in the RCT.

4.2.9 Intention-to-Treat Population

The Intention-to-Treat (ITT) population includes all subjects who are randomized into the trial, regardless of adherence to the protocol, including, for example, subjects who receive no study drug. The ITT population will be used for all exploratory outcome analyses where differences are evaluated between arms. All analyses using the ITT population

will be based on each subject's assigned treatment arm, regardless of treatment actually received.

4.2.10 Safety Population

The safety population (SAFETY) includes all subjects who receive any study drug. Reporting of results based on this population will be summarized according to treatment received. This population will be used for analysis of adverse events.

5 GENERAL ISSUES FOR STATISTICAL ANALYSES

5.1 Analysis Software

Analysis will be performed using SAS® Software version 9.4 or later whenever possible. Other software packages, including R and StatXact®, may be used for particular specialized procedures.

5.2 Methods for Withdrawals, Missing Data, and Outliers

Per the intention-to-treat principle, subjects who withdraw from the study or are lost to follow-up will have all available data used in the analysis. In the event that a substantial number of subjects are withdrawn or lost to follow-up, baseline characteristics and available information on hospital course will be reviewed and compared to subjects not withdrawn or lost, to assess empirically if these subjects differ from those remaining in the study for the scheduled treatment and follow-up time.

Outliers will be reviewed for validity. Outliers that are valid, for example, high number of vomiting episodes, will be included in all primary reports from this trial.

Due to this being a pilot study, missing data will remain missing instead of being imputed.

5.3 Multiple Comparisons and Multiplicity

As this is a pilot study, no adjustments will be made for multiple comparisons. It will be noted that no adjustments were made in any manuscript that publishes data from this pilot study.

5.4 Planned Subgroups, Interactions, and Covariates

There are no subgroup analyses planned for this pilot study.

5.5 Derived and Computed Variables

5.5.1 Enrollment Rates

The enrollment rate will be calculated as the number of subjects in the ITT population divided by the total time all sites were open for enrollment. The time (in months summarized as continuous) will be computed for each site based on the site's activation date and the site's closure date. The sum of all of these individual times is used to calculate the total time all sites were open for enrollment.

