3.2 Participant Accrual and Study Duration

This trial will enroll over a 6-month period and take place at 3 sites that are or were sites in the Pediatric Emergency Care Applied Research Network (PECARN), a federally funded network of 18 pediatric EDs that have an established and successful history of completing large-scale clinical trials in the ED. The randomized trial (stage 2) will enroll 36 patients in total (2 patients per month, per site).

4 Study Design

This pilot clinical trial is a 3-site, randomized, placebo-controlled, double-blinded trial assessing the feasibility of comparing amoxicillin to placebo in children 12 months to <6 years of age who present to the ED with CAP, a PCT<0.25 ng/mL, and who will be treated as outpatients.

5 Study Procedures

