6.2 Feasibility Outcome Analysis

The primary outcome in this pilot study is the enrollment rate per site per month. We will divide the total number of participants enrolled by the total number of months that active enrollment was occurring across sites. A 95% confidence interval will be created for this rate. We will summarize this outcome using descriptive statistics.

Secondary outcomes of the pilot study include:

- 1. Consent and drop-out rates between the two stages of consent
- 2. Parental attitudes and beliefs about trial procedures

- 3. Feasibility and usability of video chat follow-up
- 4. Lost to follow-up rates

These outcomes will be summarized in a similar fashion to the primary outcome.

[figure not shown]

Summaries of these events will be produced by arm. Continuous values will be summarized with medians (IQR) or means (SD). Categorical values will be summarized with counts and percentages. No statistical inferences between arms will be made.

In addition to these analyses, we will survey ED clinicians to refine study inclusion/exclusion criteria, including the development of specific chest radiograph criteria and outcome determination.

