9.1 Data Safety Monitoring Board (DSMB)

The study will have a Data Safety Monitoring Board (DSMB). The DSMB will have a charter, will approve the protocol prior to implementation, and will review interim analyses as applicable. The purpose of the DSMB is to advise the sponsors and Principal Investigator(s) regarding the continuing safety of study subjects and the continuing validity and scientific merit of the study. The DSMB is responsible for monitoring accrual of study subjects, adherence to the study protocol, assessments of data quality, performance of individual Clinical Center, review of serious adverse events and other subject safety issues, and review of formal interim statistical analyses of treatment efficacy.

Participant safety data will be reviewed on a regular basis. Study halting rules will be developed, and further study enrollment will be halted for DSMB review and recommendation if any halting events are reported.

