9.3.5 Unanticipated Problems (UP)

Unanticipated problems (UP) are defined as incidents, experiences, or outcomes that are unexpected, related or possibly related to participation in the study, and suggest that the research places participants at a greater risk of harm than was previously known or recognized. The site investigator will report unanticipated problems to the DCC within 24 hours of becoming aware of the event. A detailed completed report will be required to be sent to the DCC within 3 working days of the event. After receipt of the complete report, the DCC will report these unanticipated problems to the NHLBI Program Official or Project Officer in an expedited manner (as close to 24 hours as possible). In accordance with local IRB requirements, the site investigator may be required to report such unanticipated problems to the IRB in addition to notifying the Data Coordinating Center. In the event that the medical monitor believes that such an event warrants emergent suspension of enrollment in the trial, and NHLBI staff cannot be reached expeditiously, the DCC will notify the study principal investigator ([name]) and all site investigators to cease enrollment in the trial. Resumption of enrollment will not occur without consent of the NHLBI staff after discussion with the DSMB.

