9.3.6 Monitoring Serious Adverse Events

A qualified physician will be designated to fulfill the function of the medical monitor for this study. Site investigators and/or research coordinators will report serious adverse events to the DCC within 24 hours of becoming aware of the event. A detailed completed report will be required to be sent to the DCC within 3 working days of the event, and the medical monitor will assess all serious adverse events reported from site investigators.

For each of these serious adverse events, the site investigator will provide sufficient medical history and clinical details for a safety assessment to be made with regard to continuation of the trial. The medical monitor will sign off on each SAE report after review. All SAE reports will be retained at the DCC, and all SAE reports will be available for review by DSMB members and NHLBI staff. The SAE reporting process may be incorporated into the Electronic Data Capture (EDC) System in use for the study.

In the unlikely event that the medical monitor believes an unexpected and study-related SAE warrants emergent cessation of enrollment in the trial, NHLBI staff and the DSMB chairperson will be immediately consulted. If these individuals concur with the judgment of the medical monitor, or

if the NHLBI staff and the DSMB chairperson cannot be reached expeditiously, the DCC will notify the study principal investigator ([name]) and all site investigators to cease enrollment in the trial. Resumption of enrollment will not occur without consent of the NHLBI staff after discussion with the DSMB.

In accordance with local IRB requirements, the site investigator may be required to report such events to the IRB in addition to notifying the Data Coordinating Center.

After notification of the NHLBI Program Official or Project Officer, and the DSMB chairperson, of *serious, unexpected, and study-related* adverse events or unanticipated problems (UP), decisions will be made whether to continue the study without change, and whether to convene the entire DSMB for an emergent meeting. If a decision is made to suspend enrollment in the trial, this will be reported to the study investigator ([name]) and all clinical investigators, who will be instructed to report this to their local IRB.

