6 INTERIM ANALYSES

6.1 Frequency of and Timepoints for Interim Analysis

This is a pilot study evaluating the feasibility of the trial so no formal interim analyses will be performed. The DSMB will meet prior to study start and then once study is completed. If enrollment is anticipated to go longer than 8 months, then the DSMB will have the option to meet to perform a safety review of the data.

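### Does computing site time from activation and closure dates distort the primary enrollment rate if recruitment is suspended?

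*SAP*

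**What the plan says.** Protocol 6.2 defines the primary outcome as participants enrolled divided by the "total number of months that active enrollment was occurring across sites", with a 95% confidence interval. It does not define active enrollment further.

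SAP 5.5.1 divides the number in the intention-to-treat population by the time sites were open for enrollment. The time "will be computed for each site based on the site's activation date and the site's closure date", and then: "The sum of all of these individual times is used to calculate the total time all sites were open for enrollment". So the opening and closing sentences of the section give the concept (open for enrollment), and the middle sentence gives the computing rule (two dates per site). Nothing is said about suspensions, and neither date is defined.

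The protocol does allow for interruptions. Section 9.1 states that "further study enrollment will be halted for DSMB review and recommendation if any halting events are reported". Section 9.3.5 adds: "Resumption of enrollment will not occur without consent of the NHLBI staff after discussion with the DSMB". Section 9.3.6 introduces its own stopping procedure with the words "In the unlikely event that the medical monitor believes an unexpected and study-related SAE warrants emergent cessation of enrollment in the trial".

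On timing, Protocol 3.2 states: "This trial will enroll over a 6-month period". SAP 8 ends the pilot once 36 children are in the randomized stage.

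**The concern.** The two documents describe the denominator of the sole primary outcome differently. If enrollment were halted and later resumed, activation-to-closure time would include the halt and months of active enrollment would not.

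A pause is not the only route to a difference. Protocol 7.4.1 treats site initiation and close-out as events separate from enrollment, and Protocol 5.4.3 has follow-up running to Day 21 (±2 days), after accrual has ended. If closure were taken to mean administrative close-out, or if activation came before the site was ready to recruit, the SAP denominator would be too long with no pause at all. A halt that was never lifted, followed by a later closure date, would do the same.

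The plan also sits exactly on its target. The hypothesis in Protocol 6 is at least 2 per site per month, and planned accrual gives exactly 2.00. At that accrual any surplus time puts the point estimate below the hypothesized figure, and two analysts reading SAP 5.5.1 differently could report different primary results.

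**Working it through.** **Inputs.** Target of 2 per site per month, 3 sites, 6 months and a 40% share of Stage I children with PCT below 0.25 (SAP 8). Follow-up to Day 21 ±2 (Protocol 5.4.3). Pause lengths are assumptions, because the documents give none. The interval method is also an assumption: Protocol 6.2 and SAP 7.2 ask for a 95% interval for the rate without naming one.

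**The plan's own figures.**
- Randomized: 2 × 3 × 6 = 36, as stated.
- Stage I: 2/0.40 = 5 per site per month, and 5 × 3 × 6 = 90, as stated.
- Planned site-months: 3 × 6 = 18, so the planned rate is 36/18 = 2.00.

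**Formula.** Rate = n/t, with t in site-months. Exact Poisson 95% limits are χ²(0.025; 2n)/(2t) and χ²(0.975; 2n+2)/(2t). For n = 36 the limits on the count are 25.21 and 49.84.

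**Effect of counting time when a site was not enrolling** (18 site-months of true enrolling time in every row):

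| Assumed situation | t under the literal rule | Rate (95% CI) | Fall from 2.00 |
|---|---|---|---|
| No surplus time | 18 | 2.00 (1.40–2.77) | 0 |
| One site halted 1 month | 19 | 1.89 (1.33–2.62) | 1/19 = 5% |
| All sites halted 1 month | 21 | 1.71 (1.20–2.37) | 3/21 = 14% |
| All sites halted 2 months | 24 | 1.50 (1.05–2.08) | 6/24 = 25% |
| No halt; closure dated 23 days after accrual ends at each site | 20.27 | 1.78 (1.24–2.46) | 2.27/20.27 = 11% |

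The last row uses 3 × 23/30.44 = 2.27 extra site-months. The two-month row is an outer case that takes the planned 6 months to 8. The 8-month figure appears in SAP 6.1 ("If enrollment is anticipated to go longer than 8 months"), where it triggers an optional safety review. It is not a forecast of any pause.

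**When would the reading alter the message?** The upper limit falls to 2.00 when t = 49.84/2 = 24.92, that is after 24.92 − 18 = 6.92 surplus site-months, or 6.92/3 = 2.31 months at every site.

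**Sensitivity to the interval method.** Because accrual stops at 36, one can treat the count as fixed and the time as random. The upper count limit is then χ²(0.975; 72)/2 = 48.68. The planned interval becomes 1.40 to 2.70, and the threshold becomes 48.68/2 − 18 = 6.34 site-months, about 2.1 months at every site. The picture is the same.

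**Direction.** Surplus time only enlarges t. The literal rule can understate the rate but cannot overstate it.

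**The case for a change.** The case for a change is that SAP 5.5.1 is the whole derivation of the primary outcome, that halting and resuming are contingencies the protocol provides for, and that a sentence or two would settle the matter. Independent programming by two statisticians (SAP 5.6) could expose a disagreement but supplies no rule for resolving it. Because the plan sits exactly on 2.00, even a small surplus puts the point estimate below target.

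Much of this is factually right. The dates are undefined, suspensions are not mentioned, and the two readings can diverge with or without a pause. What does not follow is that the plan would mislead if carried out.

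- The section describes its own denominator as time open for enrollment. A halted site, or one that has finished accrual and is only completing follow-up, is not open in that sense. The dates are what the calculation is based on, and nothing forbids deducting an interval. Only an overly literal reading of the middle sentence, against the two around it, produces the discrepancy.
- Dual programming starts at the analysis design stage, so a question about dates would be expected to surface before results are reported.
- Whether halted time belongs in a feasibility rate is arguable. Stoppages are part of what a pilot learns, so the calendar-time rate is itself defensible, and a team that had a halt could reasonably report both.
- A shift in the point estimate decides nothing. Neither document sets a progression rule on the rate, and every interval in the table contains 2.

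**Conclusion.** The point does not call for a change. It is missing detail in SAP 5.5.1 that an analyst can fill from the section's own wording and Protocol 6.2: take the dates as the first and last days open to enrollment, and leave out any documented halt. On that reading the two documents agree.

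A difference arises only if an event the protocol calls unlikely, or an administrative reading of the dates, meets an overly literal application of the computing rule. Its size would then be modest: 5% for a one-month halt at one site, 14% for one month at all three, and 11% if closure were dated to the end of the Day 21 window. It would always run against the feasibility hypothesis. More than about 2.1 to 2.3 months of surplus time at every site would be needed before the interval excluded 2 per site per month.

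These figures assume 36 randomized over 18 enrolling site-months, illustrative pause lengths, and an exact interval that the documents do not name. The conclusion also rests on the outcome being descriptive. If the rate were later tied to a formal go/no-go threshold, the definition of the two dates would matter more.

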5.5.2 Consent Rate between Stage I and Stage II

The consent rate (which is 100% minus the dropout rate) will be calculated as the ratio of STAGE II CONSENTED and RCT ELIGIBLE (summarized as a proportion).

5.5.3 Feasibility and Usability of Video Chat Follow-Up

Secondary outcomes 3 and 4 will be analyzed among those subjects who are randomized into Stage II of the trial. On the Day 7 follow-up visit, we record the type of device used to conduct the visit. If the device is 'Mobile Phone (phone call)', then the visit will be categorized as a phone visit. If the type of device is 'Mobile Phone (video)', 'Tablet', 'Laptop', or 'Desktop computer', then the visit will be categorized as a video visit. The proportion of video visits out of all Day 7 follow-up visits will be computed. Subjects without a Day 7 visit (i.e., missed the Day 7 follow-up) will not be included in the denominator.

Among the subjects who are categorized as a video follow-up, we will also summarize the proportion of subjects where the entire assessment was able to be completed using video follow-up. Among those subjects who are categorized as a video follow-up but WERE NOT able to be completed, we will summarize the reasons why with frequencies and percentages. Among those subjects who are categorized as a video follow-up and WERE able to be completed, we will summarize the experience of the calls (video quality, sound quality, ease of use, overall experience) using frequencies and percentages. Categories of these experiences may be combined when summarizing results (e.g., combine Very Negative with Negative in a summary).

